### 1684 **Note:**

1685

1686 1687

1688

1689

1690 1691

1692

1693

1694

1695

1696

1697 1698 Protocol No.: MP-2019-004

The ALSAQ40 consists of 40 questions covering 5 domains of competence to assess the physical and mental health status of subject with ALS. The 5 domains are physical mobility, activities of daily living/independence, eating and drinking, communication, and emotional well-being, each of which constitutes a separate rating scale.

Scoring: Subjects choose appropriate descriptions for each question, and each description corresponds to a certain score (Never-0, Rarely-1, Sometimes-2, Often-3, Always or cannot do at all-4), with higher scores representing poorer ability. For each domain, the score is calculated by the following formula:

Scale score = 
$$\frac{\text{Total of raw scores of each scale item}}{\text{Maximum possible raw score of all}} \times 100$$

Example: A score is now calculated for the subject's ability to eat and drink, and the subject describes the 3 questions as: difficulty swallowing-sometimes, difficulty eating solid food-sometimes, and difficult to drink liquids-rarely, the raw total score for this domain is 2+2+1=5. The theoretical maximum raw total score for this domain is  $12 (3\times4)$ , and a score for this domain can be calculated as:  $5/12 \times 100 = 41.67$  points.

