# 1368 **8.1 Sample Size Estimation**

- The trial is an exploratory study of safety and efficacy, no statistical assumptions will be made
- and no sample calculations.
- This study is expected to enroll a total of 150 subjects, with 50 in each group.

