# 1412 8.3.4 Analysis of Secondary Efficacy Endpoint

- 1413 The following four secondary efficacy endpoints, the continuous data of each visit in different
- groups will be described using mean  $\pm$  standard deviation and median (minimum, maximum).
- 1415 Comparing with the baseline data, the paired T test is to be used to compare the within-group
- before-after differences. Analysis of variance (ANOVA) is to be used before and after treatment
- between groups. For the first secondary endpoint (endpoint event and disease exacerbation
- event), Kaplan-Meier plots will be used to describe the survival rate of patients without endpoint
- event, and Log-Rank test or non-parametric statistical method is to be used to compare the
- indicators of each group.
- 1421 (1) Proportion of endpoint events, including death, tracheotomy, invasive ventilator-assisted
- ventilation, or continuous non-invasive ventilator-assisted ventilation ( $\geq$  22 h per day for  $\geq$
- 1423 10 days);
- 1424 (2) Difference between the groups in grip strength change from baseline at Day 180;
- 1425 (3) Difference between the groups in respiratory function (%FVC) change from baseline at
- 1426 Day 180;
- 1427 (4) Difference between the groups in ALSAQ-40 scores change from baseline at Day 180.
- 1428 **8.3.5 Safety Assessment**
- Descriptive statistical analysis is mainly to be used to list the AE and SAE, drug-related AE and
- SAE that occurs in this trial, and between-group comparisons are conducted using the  $X^2$  test or
- 1431 Fisher's test.
- 1432 Descriptive statistics are to be used to summarize laboratory tests, vital signs, and
- electrocardiograms, etc. Shift tables are to be used to describe changes in normal/abnormal
- results before and after administration, such as laboratory tests, electrocardiograms, and physical
- 1435 examinations.
- 1436 **8.3.6 Interim Analysis**
- 1437 Not Applicable

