	Difficult to sleep due to shortness of breath but no need for more than two pillows during daily sleep	3
(11) Orthopnoea	Need extra pillows to fall asleep (more than 2)	2
	Can only sleep sitting up	1
	Difficulty to sleep without mechanical support	0
	None	4
	Intermittent use of ventilator	3
(12) Respiratory	Needs the ventilator every night	2
insufficiency	Needs the ventilator all day and night	1
	Invasive ventilation: intubated or a tracheostomy has been performed	0
	Total	

	Protocol No.: MP-2019-004		G	duangzhou	Magpie P	harmaceuticals Co., Ltd.
1669	Appendix 3. The amyot	rophic lateral sclerosis a	ssessment qu	uestionn	aire-40	(ALSAQ-40)
1670						
1671	NAME:	Birth Day:			Sex (I	Male/Female)
1672	Medical record number	••				
1673	Assessment Date:					
1674 1675 1676		nestionnaire as soon as parself, please get someone erested in.			•	_
1677 1678 1679 1680 1681	experienced during the likely to be the most ac experience or feelings.	sts of a number of state last 2 weeks. There are no curate for you. Please to For example, if you are ll. Please tick the box for	o right or wro	ong answ which b alk at a	ers: you	ur first response is scribes your own
1682 1683	Please try to answer exmay not seem relevant to	very question even thougo you.	gh some may	seem ra	ther sin	milar to others, or
		Never	Occasionally	Rarely	Often	Always or cannot do at all
		Physical mo	bility, 10	•	•	

	Never	Occasionally	Rarely	Often	Always or cannot do at all	
Physical mobility, 10						
1. I have found it difficult to walk short distances, e.g around the house.						
2. I have fallen over whist walking.						
3. I have stumbled or tripped whilst walking.		0				
4. I have Lost my balance whilst walking.						
5. I have had to concentrate whilst walking.						
6. Walking has tired me out.						
7. I have had pains in my legs whilst walking.						

### Version 1.1 / Jul 29, 2020 confidential Page 85 of 91

Eating and drinking, 3

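### The ALSAQ-40 form and its scoring key in Appendix 3 use different response labels in a different order, leaving one tick-box without a score (minor)

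*Protocol*

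**What the plan says.** Section 8.3.4 lists the ALSAQ-40 as the fourth secondary efficacy endpoint: "Difference between the groups in ALSAQ-40 scores change from baseline at Day 180". The trial schedule places the questionnaire at baseline and at Day 180, or at the withdrawal visit.

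Appendix 3 holds both the instrument and its scoring rule.

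- **Form.** The response columns, left to right, are "Never Occasionally Rarely Often Always or cannot do at all".
- **Key.** The note below the form assigns "Never-0, Rarely-1, Sometimes-2, Often-3, Always or cannot do at all-4".
- **Rule.** The note states that "each description corresponds to a certain score", "with higher scores representing poorer ability". An item is thus scored by its label, and nothing in the protocol scores by column position.
- **Example.** For the three eating and drinking items, answered sometimes, sometimes and rarely, the note says that "the raw total score for this domain is 2+2+1=5", which it converts to 41.67 out of 100.

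**The concern.** The form and the key should carry the same five answers. They share four, and the shared *Rarely* stands in a different place in each. A site that follows the appendix as written has no number for a tick under *Occasionally*, and the protocol's own example cannot be ticked on the protocol's own form.

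The column order adds a second risk. *Occasionally* stands before *Rarely*, whereas the key rises from *Rarely* to *Sometimes*. If the database numbered the columns 0 to 4 from left to right, or if patients took the columns to be an ascending scale, the two lower-middle answers would be misplaced relative to the key. At stake is the measurement quality of one named secondary endpoint.

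**Working it through.** **Inputs.** All are from Appendix 3: the column headings, the key, the worked example, and the domain sizes printed on the form (physical mobility 10, eating and drinking 3, communication 7, emotional well-being 10). Activities of daily living is taken as the remainder: 40 − (10 + 3 + 7 + 10) = 10.

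**Formula.** Domain score = sum of item scores ÷ (4 × number of items) × 100.

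**Step 1: reproduce the protocol's figure.** (2 + 2 + 1) ÷ 12 × 100 = 41.67. This agrees with the note.

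**Step 2: set form and key side by side.**

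| Column on form | Label on form | Score by the key's labels | Score if coded by position |
|---|---|---|---|
| 1 | Never | 0 | 0 |
| 2 | Occasionally | none given | 1 |
| 3 | Rarely | 1 | 2 |
| 4 | Often | 3 | 3 |
| 5 | Always or cannot do | 4 | 4 |

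The key's remaining entry, *Sometimes* = 2, has no column. Only columns 2 and 3 are affected.

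**Step 3: score the example on the printed form.** Assume that *Occasionally* stands for *Sometimes*, which the protocol does not say. The ticks are then *Occasionally*, *Occasionally*, *Rarely*.

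- By label: 2 + 2 + 1 = 5, and 5 ÷ 12 × 100 = 41.67.
- By position: 1 + 1 + 2 = 4, and 4 ÷ 12 × 100 = 33.33.
- Difference: 8.33 points. The two *Occasionally* items each lose a point and the *Rarely* item gains one, so the errors partly cancel.

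**Step 4: shift per affected item.** One raw point moves a domain by 100 ÷ (4 × number of items):

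| Domain size | Shift per affected item |
|---|---|
| 3 items (eating and drinking) | 100 ÷ 12 = 8.33 |
| 7 items (communication) | 100 ÷ 28 = 3.57 |
| 10 items (the other three) | 100 ÷ 40 = 2.50 |

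Steps 3 and 4 apply only if position coding, or an equivalent reading by patients, actually occurs.

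**The case against.** The strongest reply is that the protocol has already settled how to score. The note scores by description, and its example gives *Rarely* a 1. Four of the five labels match exactly, so by elimination *Occasionally* must be *Sometimes*, worth 2, and that reading returns the protocol's 41.67. The trial is run in China, so patients presumably complete a Chinese form, and the English header may be no more than a translation slip. The endpoint is the last of four secondary endpoints in an exploratory study for which "no statistical assumptions will be made".

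Most of this stands, and it rules out several stronger readings that a reader might infer:

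- **That *Rarely* officially scores either 1 or 2.** It does not. The rule makes it 1, and 2 needs an assumption about the eCRF or about how patients read the columns.
- **That the endpoint is corrupted.** The documents show a risk, not an effect. Neither the form used at sites nor the eCRF coding can be seen.
- **That the affected answers are where most patients start.** The protocol gives no baseline distribution of ALSAQ-40 answers. Obvious dysphagia is an exclusion criterion, so many eating and drinking items may be *Never*, which is unaffected.
- **That a domain would move by 25 points.** This is the arithmetic ceiling. It needs every item of a domain to sit in the same affected category, and mixed answers partly cancel.
- **That the repeated column header proves the order.** Both appearances sit above the same first block of items, so the repetition is weak evidence.

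What survives is the difference in wording. A broken table can displace a heading but does not turn *Sometimes* into *Occasionally*. Pairing the two by elimination is sensible, but the protocol should state it rather than leave it to each site.

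**Conclusion.** The point holds as an internal inconsistency in Appendix 3. Followed as written, the key leaves one of the five printed answers unscored, and the printed order is not the key's rising order.

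Its size is conditional. If items were coded by column position, or if patients read the columns as ascending, each affected item would shift its domain by 8.3, 3.6 or 2.5 points according to domain length, and the protocol's example would fall from 41.67 to 33.3. The example comparison also assumes that *Occasionally* stands for *Sometimes*.

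All arms use the same form under blinding, so the expected harm is noise and a distorted scale. The documents do not support a claim of bias toward an arm. The primary endpoint, ALSFRS-R, is untouched. Severity: minor.

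**What to change.** Use the key's five labels, in the key's rising order from *Never* through *Rarely*, *Sometimes* and *Often* to the top category, on the form, in the key, in the worked example and in the eCRF code list. Confirm which version the sites and the eCRF actually use, including the Chinese form.

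If forms with the mismatched columns have already been completed:

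1. Fix the score for *Occasionally* in writing before unblinding. Rescoring by label is not possible until this is done.
2. Flag those forms in the database.
3. Run a sensitivity analysis under column-position coding (*Occasionally* = 1, *Rarely* = 2). Rescoring cannot recover how a patient understood the columns, and this analysis shows whether the result depends on it.

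The cost is a correction to one form and one code list, plus one short check with the sites. The sensitivity analysis is needed only if affected forms exist.

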## **Appendix 4. Mini-Mental State Examination (MMSE)**

Protocol No.: MP-2019-004

1700

I'm going to ask you some questions to check your attention and memory. Most of them are easy. (Examiner: Record the answers and circle the scores. Those who don't know are counted as wrong.)

		Right	Wrong
1.What is the year?	Year	1	5
2.What is the season?	Season	1	5
3. What is the day of the week?	Day	1	5
4. What is the date?	Date	1	5
5. What is the month?	Month	1	5
6. Can you please tell me where we are?			
For example, what province (city) are we in?	Province (City)	1	5
7. What district (county) is here?	District (county)	1	5
8.What street (township) is here?	Street (township)	1	5
9. What floor of the building are we on?	Floor	1	5
10. What is this place?	Address	1	5
	(Address or building name)		

11. I am going to name three objects. When I am finished, I want you to repeat them. Remember what they are because I am going to ask you to name them again in a few minutes. (Examiner: Say the following words slowly at one-second intervals):

"Ball" "Flag" "Tree"

Please repeat the three items for me.

Refuse

(Only score first attempt)

Right Wrong to answer

14. (Examiner: show wristwatch) What is this called?

(Only score first attempt)

	Right	Wrong	Say can't do it	Refuse to do it			
Wristwatch	1	5	7	9			
14. (Examiner: show pencil) What is this called?							
Pencil	1	5	7	9			
15. Now I am going to say a phrase, and Chinese)"	d please repea	at it clearly. The ph	rase is:"forty-four stone	lions (in Mandarin			
(Allow only one trial. Only correct and ea	xact words co	unt for one point.)					
forty-four stone lions (in Mandarin Chinese)	1	5	7	9			
16. (Examiner: Hand Card 1 to the subject	ct) Please do v	what is written on th	is card.				
	Right	Wrong	Say can't do it	Refuse to do it			
Close your eyes	1	5	7	9			
17. (Examiner: Say the following paragraph and give the subject a piece of paper; do not repeat the instructions or demonstrate) Please take this piece of paper in your right hand, then fold it in half with both hands and put it on your lap.							
	Right	Wrong	Say can't do it	Refuse to do it			
Take the paper in right hand.	1	5	7	9			
Fold the paper in half	1	5	7	9			
Put the paper on lap	1	5	7	9			
18. Please say a complete and meaningful sentence. (Requirements: The sentence must have subject and verb, make sense, and record the sentence)							

Meeting the

requirements

Not meeting the

requirements

Refuse to do it

Record	1 5	5 9

19. (Examiner: Hand Card 2 to subject) This is a picture, please copy it as it is.

(Requirements: The subject must draw a four-sided figure between two five-sided figures.)

	Right	Wrong	Say can't do it	Refuse to do it
Record	1	5	7	9
Card 1	"Please close your eyes"			

[figure not shown]
Card 2

1702

1703

1704

1705

1701 Scoring Guidelines:

The scale consists of 19 questions with 30 subitems. Correct answers or operations are scored as "1", wrong answers are scored as "5" and refusals or say can't do it are scored as "9" and "7". When calculating the score, the sum of all items (and subtests) marked "1", i.e., the number of items/subtests answered/operated correctly, is counted and is called the total MMSE score, which ranges from 0 to 30.
